10.3 Reporting Procedures

10.3.1 Adverse Events

AEs will be followed until resolution even if this extends beyond the study-reporting period. Resolution of an AE is defined as the return to pretreatment status or stabilization of the condition with the expectation that it will remain chronic. All AEs collected during the study will be documented on the appropriate CRF. CHOP and PITT are responsible for reporting adverse events to their local IRB in accordance with the local IRB requirements. The PI or a co-investigator at each site will determine the proper response per the research protocol—i.e.: changing therapy, initiating new therapy, or having the subject discontinue study product (of days six - ten).

10.3.2 Serious Adverse Events

If in the opinion of a study physician investigator (PI or co-investigator) the event meets the criteria of a SAE the following procedures will occur.

All SAEs will be:

-
- Recorded on the DMID SAE reporting form and the SAE CRF by study staff.
 - Reviewed by PI or co-investigator, who will assess the event’s relationship to study product or procedures. All SAEs will be assessed for relationship to the study research procedures. A causal relationship means that the study participation caused (or is reasonably likely to have caused) the event. This usually implies an association in time between a study procedure and the event.
 - Followed by PI or co-investigator until satisfactory resolution or until the PI or co-investigator or deems the event to be chronic or the subject to be stable.
 - If an SAE has not resolved at the time of the initial report, a follow-up SAE reporting form must be submitted and a follow-up SAE CRF must be completed. SAEs will be followed until resolution or stabilization if the event is expected to remain chronic.

Any AE that meets a protocol-defined serious criterion must be submitted immediately (within 24 hours of site awareness) on an SAE form to the DMID Pharmacovigilance Group, at the following address:

**DMID Pharmacovigilance Group
Clinical Research Operations and Management Support (CROMS)
[name]
[name]
SAE Hot Line: [name] (US) or [name] (outside US)
SAE FAX [contact] (US) or [name] (outside US)
SAE Email Address: [contact]**

All SAEs regardless of relationship will be recorded on the SAE form and sent by fax within 24 hours of site awareness of the event. Other supporting documentation of the event may be requested by the DMID Pharmacovigilance Group and should be provided as soon as possible. This may include all relevant new or reassessed information (e.g. concomitant medication, medical history). Follow-up information will be submitted to the IRB and DMID Pharmacovigilance Group who will provide this to the DMID medical monitor and clinical program manager. All SAEs will be followed until either resolved or stable.

The DMID medical monitor and clinical protocol manager will be notified of the SAE by the DMID Pharmacovigilance Group. The DMID medical monitor will review and assess the SAE for regulatory reporting and potential impact on study subject safety and protocol conduct.

At any time after completion of the study, if the investigator becomes aware of an SAE that is suspected to be related to study product, the investigator will report the event to the DMID Pharmacovigilance Group.

Serious adverse events will be reported to the independent Data Safety Monitoring Board (DSMB) according to the guidelines and schedule established by that group in the charter. All adverse events and safety data will be reported to the DSMB through regularly scheduled reports.

The Principal Investigator will promptly notify the IRB of all study on-site SAEs and other unanticipated problems related to research using the CHOP Internal SAE reporting form and in accordance with the following timeline. External SAEs that are unexpected and related to the study intervention should be reported as received using the External SAE form (if applicable).

Table 7: IRB Adverse Event Notification

Type of Internal Adverse Event	Initial Notification (Phone, Email, Fax)	Written Report
Internal (on-site) SAEs Death or Life Threatening	24 hours	Within five calendar days
Internal (on-site) SAEs All other SAEs	72 hours	Within five calendar days
Unanticipated Problems Related to Research	72 hours	Within five calendar days
All other Events	N/A	As per local IRB requirement

10.3.3 Regulatory Reporting for Studies Conducted Under DMID-Sponsored IND

Following notification from the investigator, DMID, the IND sponsor, will report any suspected adverse reaction that is both serious and unexpected. DMID will report an adverse event as a suspected adverse reaction only if there is evidence to suggest a causal relationship between the drug and the adverse event. DMID will notify FDA and all participating investigators (i.e., all investigators to whom the sponsor is providing drug under its INDs or under any investigator’s IND) in an IND safety report of potential serious risks from clinical trials or any other source, as soon as possible, but in no case later than 15 calendar days after the sponsor determines that the information qualifies for reporting as specified in 21 CFR Part 312.32. DMID will also notify FDA of any unexpected fatal or life-threatening suspected adverse reaction as soon as possible but in no case later than 7 calendar days after the sponsor’s initial receipt of the information. Relevant follow up information to an IND safety report will be submitted as soon as the information is available. Upon request from FDA, DMID will submit to FDA any additional data

or information that the agency deems necessary, as soon as possible, but in no case later than 15 calendar days after receiving the request.

All serious events designated as “not related” to study product(s), will be reported to the FDA at least annually in a summary format.

10.4 Type and Duration of Follow-up of Subjects after Adverse Events

After the initial SAE report, the investigator will follow each subject and provide further information to the DMID medical monitor on the subject’s condition. All AEs documented at a previous visit/contact and are designated as ongoing, will be reviewed at subsequent visits/contacts. All AEs will be followed until resolution, until the condition stabilizes, until the event is otherwise explained, or until the subject is lost to follow-up. Once resolved, the appropriate AE source document and CRF pages will be updated. The investigator will ensure that follow-up includes any supplemental investigations as may be indicated to elucidate the nature and/or causality of the AE. This may include additional laboratory tests or investigations, histopathological examinations, or consultation with other health care professionals.

All AEs reported in this study will be followed until resolution or until the investigator and the clinical monitor are in agreement that the AE has stabilized and no additional follow-up is required. This requirement indicates that follow-up may be required for some events after the participant discontinues participation from the study. These events will be reported to the IRB annually, as well as the DSMB, according to the frequency defined by the DSMB Charter.

10.5 Halting Rules

Because of the masked nature of the study design, the treatment failure for UTI cannot be monitored in the short-course arm alone. However, we will monitor the failure rate separately in BOTH arms for the first 100 subjects in each arm. To ensure patient safety the following early halting rule will be applied separately to each study arm:

Stop accrual/suspend if at any stage:

- 3 among the first 16 patients experience a treatment failure
- 5 among the first 23 patients experience a treatment failure
- 6 among the first 29 patients experience a treatment failure
- 7 among the first 36 patients experience a treatment failure
- 8 among the first 43 patients experience a treatment failure
- 9 among the first 49 patients experience a treatment failure
- 10 among the first 56 patients experience a treatment failure

11 among the first 63 patients experience a treatment failure
12 among the first 69 patients experience a treatment failure
13 among the first 76 patients experience a treatment failure
14 among the first 83 patients experience a treatment failure
15 among the first 89 patients experience a treatment failure
16 among the first 96 patients experience a treatment failure
17 among the first 100 patients experience a treatment failure

The halting probabilities (based on sequential Bernoulli outcomes) of the halting rule above are displayed in Table 8 below.

Table 8: Probability of stopping in terms of true treatment failure rate for UTI and number of patients enrolled on the study

No. of Subjects	Treatment failure rate		
	5%	15%	20%
15	0.04	0.40	0.60
20	0.04	0.44	0.65
25	0.04	0.46	0.69
30	0.04	0.48	0.72
35	0.04	0.51	0.75
40	0.04	0.52	0.78
50	0.04	0.56	0.82
60	0.04	0.59	0.86
70	0.04	0.61	0.88
80	0.04	0.63	0.90
90	0.04	0.65	0.92
100	0.04	0.67	0.93

Thus, if the true treatment failure rate is 5%, then the probability of terminating accrual at the 25th patient is 4%. Note that this probability converges to 4% and will be expected to remain at this value for the rest of the study. In contrast, if the true treatment failure rate is 15%, the probability of stopping accrual at the 25th patient is 46%.

In addition, any SAE considered related to the study procedures or products will be reported to the DMID Medical Monitor and DSMB members and a safety evaluation will be conducted by electronic review. Upon reviewing the event members of DSMB or/and DMID MM may request an ad hoc meeting to further discuss it.

The ad hoc meeting of the DSMB will be organized to determine if the study may proceed without changes, should be revised, or even terminated. The PI and/or DMID may request ad hoc meetings of the DSMB

The IRB, NIAID, and the FDA as part of their duties to ensure that research subjects are protected; may discontinue the study at any time. Subsequent review of serious, unexpected and related adverse events by the DMID Medical Monitor, DSMB, the ethics review committee or IRB, NIAID, the FDA, and other regulatory authorities may also result in suspension of further trial interventions/administration of study agent at a site. The FDA, other regulatory authorities, and NIAID retain the authority to suspend additional enrollment and study product administration for the entire study as applicable.

If rates of study product-related SAEs are unexpectedly high, the DMID medical monitor will promptly conduct a safety review involving the DSMB to determine if suspension of enrollment is warranted.

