3.2 Sample size determination and power calculations

The primary aim of this study is to determine whether short-course antimicrobial therapy (five days) is non-inferior to standard-of care antimicrobial therapy (10

days) for the treatment of UTI in children with respect to reinfection of UTI through TOC visit Day 11-14. The treatment failure rate under the standard of care, R_0 , is expected to be 5%. This estimate is based on data from previously published studies [1, 2]. The power and sample size calculations are based on the assumption that recurrence under the short-course therapy, R_{SC} , will range from 5% to 9%.

In the non-inferiority test, on which power and sample size are based, the null hypothesis that short-course therapy is inferior to standard-of-care therapy is tested against the alternative that short-course therapy is non-inferior. That is, $H_0: R_{SC} > R_0 + \delta$ is tested against $H_a: R_{SC} \leq R_0 + \delta$, where δ is the “interval of equivalence,” the range in which the treatment failure rates of the two therapies would be considered clinically equivalent. We believe that an interval of equivalence of 5% would be clinically acceptable; a success rate of 95% for the standard-of-care therapy group when compared to 90% for the short-course therapy group. For all power and sample size calculations, the significance level (chance of incorrectly rejecting the null hypothesis) is $\alpha = 0.05$.

Table 1 gives the power for testing the non-inferiority hypothesis with a sample size of 300 evaluable subjects per arm and with equivalence intervals (i.e., δ) ranging from 2% to 5%. With 300 subjects per arm, there would be 87% power with $R_{SC} = 5\%$ and $\delta = 5\%$. The power decreases as either the equivalence interval decreases or as R_{SC} increases; in other words, as the recurrence rates of the two regimens become more similar, large sample sizes are required to discriminate between them.

Table 2 gives the sample sizes required to obtain 80% power with the same parameters for R_{SC} and δ . A sample size of 235 per arm is sufficient for 80% power with $R_{SC} = 5\%$ and $\delta = 5\%$, while larger sample sizes are required for larger values of R_{SC} or smaller values of δ . Finally, Table 3 gives the sample sizes required to obtain 90% power; a sample size of 326 subjects per arm would be required for 90% power with $R_{SC} = 5\%$ and $\delta = 5\%$.

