4.1 Interim Analysis

After half of the subjects (373 subjects) have enrolled, an interim analysis for the primary endpoint of treatment failure rate will be performed. This efficacy analysis will test the null hypothesis that the treatment failure rate under short-course therapy is less than or equal to that of standard-of-care therapy; the alternative hypothesis is that the failure rate under short-course therapy is greater than using standard-of-care therapy. This test will be one-sided test of hypothesis of equal treatment failure rates between the short-course therapy and standard-of-care therapy with $\alpha=0.05$. We will calculate the difference in treatment failure rates between short-course therapy and standard-of-care therapy, and a one-sided 95% lower confidence limit using normal approximation for large samples. If the lower confidence limit exceeds zero, we will conclude that short-course therapy has a significantly higher failure rate than standard-of-care therapy. Since the interim analysis is for superiority of standard-of-care therapy and the final efficacy analysis is for non-inferiority of short-course therapy, there is no impact of the interim analysis on the Type I error of the final efficacy analysis and thus no adjustments to the significance level are required.

In addition, conditional power estimates may be calculated. The conditional power analysis is a re-assessment of the power given the results of the study to date. If the recurrence rate for short course therapy is smaller than expected relative to standard therapy, then there would be high conditional power; if the recurrence rate for short course therapy is greater than expected relative to standard therapy, then there would be lower power than initially expected. The need for this analysis will be

decided in conjunction with the DSMB, along with other data to be presented to the DSMB.

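### Table 8 gives the halting probability for one arm but words it as the chance of stopping accrual to the study; with a true 5% failure rate in both arms, the chance that at least one arm triggers is about 8.7%, not 4%

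*Protocol*

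**What the plan says.** Protocol section 10.5 states that "we will monitor the failure rate separately in BOTH arms for the first 100 subjects in each arm" and that "the following early halting rule will be applied separately to each study arm". The instruction is "Stop accrual/suspend if at any stage", followed by 14 boundaries running from "3 among the first 16 patients experience a treatment failure" to "17 among the first 100 patients experience a treatment failure".

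Table 8 then lists stopping probabilities for true failure rates of 5%, 15% and 20%. Its title ties them to the number of patients enrolled on the study. The 5% column reads 0.04 in every row. The text below the table says that "if the true treatment failure rate is 5%, then the probability of terminating accrual at the 25th patient is 4" per cent, and that the figure will stay there for the remainder of the study. Neither document gives a probability that covers both arms together.

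SAP section 3.2 says that "a sample size of 326 subjects per arm would be required for 90% power", with 5% failure in both arms and a 5-point margin. It then adds about 11% for losses. It does not mention the halting rule. SAP section 4.1 describes an interim test for harm: "If the lower confidence limit exceeds zero", the conclusion is that short-course therapy has the higher failure rate. The section does not say what happens to the trial after that.

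**The concern.** The rule has two chances to fire, one in each arm. The documents do not say in so many words that a trigger in one arm stops accrual to both. But allocation is masked and 1:1 from a central system, so accrual cannot sensibly halt in one arm and go on in the other. The chance of an unwarranted stop or pause is therefore the chance that either arm crosses. Someone who takes the 4% as the study-level figure, as its wording invites, would plan for about half the real chance of a false alarm at the failure rate the design itself assumes. If a trigger were also final, the study would have less power than the fixed-sample calculation gives.

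**Working it through.** **Inputs.** The 14 boundaries, the 100-patient window per arm and the Bernoulli basis come from Protocol 10.5. The 5% failure rate and 5-point margin are in Protocol 12.2 and SAP 3.2. The one-sided 0.05 level is in SAP 4.2.2. SAP 3.2 gives 326 evaluable per arm. Protocol section 5 gives 672 evaluable in total, or 336 per arm.

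**Step 1: reproduce Table 8.** Take one arm, with each patient failing independently with probability p. The limit is 3 failures up to patient 16, 5 up to patient 23, and so on to 17 up to patient 100, checked after every patient. At p = 0.05 the first boundary alone gives

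P(X ≥ 3 | n = 16) = 1 − [0.95^16 + 16(0.05)(0.95^15) + 120(0.05²)(0.95^14)] = 1 − (0.4401 + 0.3706 + 0.1463) = 0.043.

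The exact recursion over all boundaries gives:

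| Patients in the arm | 5%: computed / stated | 15%: computed / stated | 20%: computed / stated |
|---|---|---|---|
| 15 | 0.036 / 0.04 | 0.396 / 0.40 | 0.602 / 0.60 |
| 25 | 0.0436 / 0.04 | 0.463 / 0.46 | 0.686 / 0.69 |
| 50 | 0.0445 / 0.04 | 0.562 / 0.56 | 0.824 / 0.82 |
| 100 | 0.0446 / 0.04 | 0.666 / 0.67 | 0.933 / 0.93 |

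The rows not shown also agree within 0.01. Checking only at the listed patient numbers would give zero at row 15, so the table was built with a check after every patient. The two ways of checking agree at patient 100. Table 8 is a one-arm table, and it is correct as one.

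**Step 2: either arm.** With independent arms, P(at least one trigger) = 1 − (1 − p₁)(1 − p₂). With 5% in both arms:

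- by patient 25 per arm: 1 − (1 − 0.0436)² = 0.085
- by patient 100 per arm: 1 − (1 − 0.0446)² = 0.087

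The rounded 0.04 would give 1 − 0.96² = 0.078. Simulation of 400,000 trials at each sample size gave 0.087 to 0.088. Of the 0.0446 per arm, 0.0429 has accrued by patient 16, so a false trigger would usually come early. With the same rate in both arms, the values at patient 100 are 1 − (1 − 0.6656)² = 0.888 at 15% and 1 − (1 − 0.9325)² = 0.995 at 20%.

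**Step 3: power, conditionally.** The fixed-sample formula is n = (1.645 + 1.282)² × 2(0.05)(0.95) / 0.05² = 8.57 × 38, or 326 per arm after rounding up with unrounded normal quantiles. This equals the SAP figure, so it contains no term for halting. The simulation used an unpooled one-sided 95% upper limit of at most 0.05 for success, and an interim look at half the evaluable subjects per arm:

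| Reading | 326 per arm | 336 per arm |
|---|---|---|
| No halting, or every suspension lifted | 0.90 | 0.91 |
| Every trigger final | 0.82 | 0.83 |
| Every trigger final, and the interim harm conclusion also ends the trial | 0.80 | 0.81 |

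**The case against.** The strongest reply is that no cell of Table 8 is wrong. Section 10.5 says the rule is applied separately to each arm, the monitoring window is stated per arm, and the rows stop at 100, which matches that window. A careful reader can work out the unit, and the DSMB includes a biostatistician. This stands, and it makes the fault one of labelling plus a missing figure, not a miscalculated table. It does not rescue the table title or the sentence beneath it, because both speak of accrual and of the study.

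A reader might go further and infer that the 90% power is wrong. The documents do not support that. The instruction "Stop accrual/suspend if at any stage" is not said to be final. Protocol 10.6 says only that the DSMB may meet more often once halting rules come into play, and that it advises the sponsor. The later text of 10.5 lets an ad hoc DSMB meeting allow the study to go on unchanged, although that text is framed around serious adverse events. Neither Protocol 12.3 nor SAP 4.1 says the interim harm conclusion ends the trial. Leaving a non-binding safety guideline out of a fixed-sample power calculation is ordinary practice.

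A reader might also infer that the oversight bodies were given a study-level risk understated by half. No explicitly two-arm figure is given to anyone, and the DSMB charter is not among the documents. What can be said is that the published wording invites that misreading.

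**Conclusion.** The point holds as one of labelling and completeness, and its severity is minor. Section 10.5 presents a one-arm probability as the chance of stopping accrual. At the study level, with 5% true failure in both arms, the chance of at least one trigger is about 8.5% by patient 25 per arm and 8.7% by patient 100 per arm. This assumes independent arms, Bernoulli outcomes assessed in order, and that a trigger in either arm affects accrual to the whole trial.

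The effect on power is a range and not a demonstrated error. It runs from no loss, if a trigger is a suspension that is lifted, to about 8 points if every trigger is final, and to about 10 points if the interim harm conclusion also ends the trial. The documents do not say which reading applies.

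**What to change.** - In Protocol 10.5, add per arm to the title of Table 8 and to its row heading.
- Add an either-arm column, about 0.09 when the true rate is 5% in both arms.
- Reword the sentence below the table to say about 4.5% per arm, and about 8.7% that at least one arm triggers, by the end of monitoring when both true rates are 5%.
- Have the sponsor and DSMB reconcile "Stop accrual/suspend if at any stage" with the later text of 10.5 and with 10.6, so that the consequence of a trigger is stated. SAP 4.1 should likewise state the consequence of the interim harm conclusion. Which consequence applies is for them to decide.
- Only if a trigger is declared final, restate power against the matching sample size: about 82% at 326 per arm (fixed-sample 90%) or about 83% at 336 per arm (fixed-sample 91%). If the interim conclusion also ends the trial, the figures are about 80% and 81%. If a trigger is a suspension that is lifted, the power statement needs no change.

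The cost is wording in the protocol and SAP, plus one published figure that becomes less favourable. No boundary, sample size or analysis changes.

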10.6 Safety Oversight

Safety oversight will be under the direction of a DSMB which will consist of at least 3 voting members including a biostatistician experienced in statistical methods for clinical trials and a clinician with relevant expertise. The DSMB will operate under the rules of a DMID-approved charter written at the organizational meeting of the DSMB. At this time, each data element that the DSMB needs to assess will be clearly defined. During the course of the study, the DSMB will meet at least annually to assess safety and efficacy data on each arm of the study. The DSMB will review aggregate safety data for increased rate of occurrence of serious suspected adverse reactions. If halting rules are initiated, more frequent meetings may be held. The DSMB will advise DMID of its findings.

Unmasking intentional or unintentional is strongly discouraged and must be approved by DMID. However, if such event(s) occur, the Principal Investigator and co-Investigators will notify the DMID immediately, so that the DSMB can be made aware and assess the potential impact of the unmasking on the overall integrity of the study.

